## 1. Study Protocol

Potential participants were Veterans with recurrent binge eating seeking weight loss were recruited from VA's Weight Management Program, MOVE! at two VA sites: West Haven, CT and Northampton, MA between January 2018 and May 2022. As recruitment for this study was underway during the COVID-19 pandemic, Veterans were first recruited from in-person MOVE! orientation sessions between January 2018 and March 2020 and then additionally from VA's remote TeleMOVE! program starting in July 2020. Eligibility required age 21+, Body Mass Index (BMI) $\geq$ 25, and DSM-5 clinical/subclinical BED. Exclusions were: attendance of more than 4 MOVE! group sessions in the prior year, active psychosis or suicidal ideation, medical or psychiatric illness or cognitive deficits that interfere with providing consent or completing assessments, and pregnancy or lactation. The study received IRB approval by the VA Connecticut Healthcare System, which provides oversight for both West Haven, CT, and Northampton, MA facilities.

### 1.1 Measures

Participant assessments were conducted by blind assessors at baseline, post-treatment (3-months), and 6- and 12-month follow-ups (9- and 15-months after randomization). Primary outcomes included eating pathology and binge eating, secondary outcomes included measures of mental health, quality of life, and other eating behavior. Weight outcomes were explored. Participants were compensated \$25 for baseline, \$40 for post-treatment, and \$50 and then \$60 for follow-up assessments.

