### 1.2 Diagnostic and Primary Outcomes: Eating Pathology and Binge Eating

Eating Disorder Examination-Interview 17.0th Edition (EDE)[1] is the structured diagnostic interview that is considered the gold-standard to diagnose, and assess the symptoms of, eating disorders including binge eating and eating disorder pathology. Binge Frequency was defined as the average number of monthly binge episodes for the past three months at baseline, and average number of monthly binge episodes for the past month at post-treatment and follow-up assessments. Binge Remission was defined as zero binge episodes in the previous month.

Eating Disorder Examination-Self-report Questionnaire (EDE-Q)[2] is the self-report version of the more intensive EDE interview. Research has documented that the EDE-Q performs well as a measure of change in treatment trials[3] and has adequate convergence with the interview format[4, 5]. The EDE-Q generates the same frequency data for binge eating in the past 28 days, as well as a total score for overall eating pathology and subscale scores for dietary restraint, weight concern and shape concern, and eating concern.

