## 2. Statistical Analysis Plan

Baseline characteristics were compared between the treatment groups using ANOVA and chi-squares as appropriate in order to determine the level of success of the randomization. Distributions of outcomes were examined to determine if assumptions of specific model types were met. Change of model type as well as transformation of the data were considered if model assumptions were not met. Mixed-effects models, a method for statistical modeling that uses both fixed effects and random effects, were used to examine continuous outcomes such as eating pathology binge eating frequency, mental health symptoms, and percent weight loss for completer, as well as intent-to-treat (all randomized persons), analyses. Logistic regression models were used for categorical outcomes such as binge remission and achieving clinically meaningful weight loss (i.e., 5% weight loss or greater). The outcomes were transformed to approach normality as needed and models controlled for treatment, time, gender, age, and baseline BMI.

*2.1 Cohort (in-person vs remote) analyses.* There were 40 (37%) subjects in cohort 1 and 69 (63%) in cohort 2. All the analyses with cohort (categorical variable) added to the models were run and conclusions were substantively the same.

*2.2 Missing Data.* Missing data was minimized by having participants complete with assistance of research assistants. The mixed-effects models addressed missing data for continuous outcomes as the modeling makes use of all available data for each participant, even when there are different numbers of observations. [79]

*2.3 Missingness analyses.* We focused on the missingness of the primary outcome averages binge per month (over past 3 months). Outcome was missing for 11.9% of subjects at month 3, 19.3% at month 9, and 24.8% at month 15. Overall, these 3 timepoints, 35.8% of subjects had incomplete outcome data (missing outcome at any of timepoints). There was no evidence of a difference between groups in missingness at any timepoint or overall (all p-values $\geq$ .10).

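### The primary tier holds several unranked outcomes with no multiplicity rule, tested contrast or lead population; separately, Section 2.3 words the post-baseline binge window differently from Section 1.2

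*Combined protocol and SAP*

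**What the plan says.** **Outcomes.** Section 1.1 states "Primary outcomes included eating pathology and binge eating", in the plural and by domain. Section 1.2, whose heading covers primary outcomes, describes these measures:

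- EDE binge frequency, which after baseline is the "average number of monthly binge episodes for the past month at post-treatment and follow-up assessments"; three months are used at baseline only.
- Remission: "Binge Remission was defined as zero binge episodes in the previous month".
- EDE-Q scores: a 28-day binge count, and "a total score for overall eating pathology and subscale scores for dietary restraint, weight concern and shape concern, and eating concern".

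**Analysis.** Section 2 (opening paragraph) applies mixed-effects models to continuous outcomes "for completer, as well as intent-to-treat (all randomized persons), analyses" and logistic regression to categorical ones. On model content it says "models controlled for treatment, time, gender, age, and baseline BMI". No treatment-by-time term, baseline value of the outcome, tested contrast or lead visit is mentioned.

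**Missing data.** Section 2.2 says "The mixed-effects models addressed missing data for continuous outcomes as the modeling makes use of all available data for each participant". Section 2.3 says "We focused on the missingness of the primary outcome averages binge per month (over past 3 months" and then gives missingness at months 3, 9 and 15. It finds no evidence that missingness differed between the groups. Section 2.4 reports that conclusions held after further predictors of missingness were added.

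The documents state no significance level, sidedness, sample-size calculation or multiplicity procedure.

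**The concern.** A plan should let a reader say, before seeing results, which test decides the trial. Here at least three measures could each be presented as the primary finding, and for each the effect could be an overall difference or a difference at one of three visits. If any one significant result is enough, the error rate for the primary claim exceeds the level of each test.

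The population label matters because 35.8% of participants had incomplete binge data, so completer and intent-to-treat results need not agree.

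The window matters less but is not empty. At month 3 a three-month look-back would cover the whole three-month treatment period, and a past-month look-back only its end. The two measure different things, so the text should give one.

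**Working it through.** **1. Counts.** The plan has no design figure to reproduce, so its stated counts were checked instead.

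- Randomized: 101 + 8 = 109 by stratum and 40 + 69 = 109 by cohort.
- Missing: 13/109 = 11.9% (month 3), 21/109 = 19.3% (month 9), 27/109 = 24.8% (month 15).
- Incomplete at any of these visits: 39/109 = 35.8%.

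These agree with Sections 1.6, 2.1 and 2.3.

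**2. Error rate.** Assumptions, none of them in the documents: two-sided 0.05 per test, one test per outcome, any one rejection supports a primary claim, all nulls true, and jointly normal test statistics. The three outcomes are EDE binge frequency, binge remission and EDE-Q total.

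If independent: 1 − (1 − 0.05)^m, which is 9.75% for m = 2 and 14.26% for m = 3.

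With common correlation ρ and c = 1.96:

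1 − ∫ φ(u) [Φ((c − √ρ u)/√(1−ρ)) − Φ((−c − √ρ u)/√(1−ρ))]^m du

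| ρ | 2 tests | 3 tests |
|---|---|---|
| 0 | 9.75% | 14.26% |
| 0.3 | 9.51% | 13.62% |
| 0.5 | 9.07% | 12.54% |
| 0.7 | 8.35% | 10.92% |
| 0.9 | 7.04% | 8.36% |

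The upper end is unlikely, because frequency and remission come from the same past-month episodes. As an illustration, let those two correlate 0.5 to 0.85, and let each correlate 0.3 to 0.7 with EDE-Q total. Simulation with 6 million draws then gives 10.3% to 13.3%.

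**3. Effect of Holm.** The first step for three outcomes is 0.05/3 = 0.0167. With all nulls true, the chance of any rejection is 1 − (1 − 0.0167)³ = 4.9% if independent, and 3.7% to 4.7% in the illustration above.

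**4. The contrast.** The listed terms suggest a single treatment effect, but the text does not say whether baseline is a level of time. Suppose it is, with no interaction, complete data and equal visit weights. A constant post-baseline difference δ is then estimated as (0 + δ + δ + δ)/4 = 0.75δ. The contrast therefore has to be stated with baseline handled explicitly.

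**5. The window, side by side.** Section 1.2 defines three months at baseline and the past month afterwards. Section 2.3 attaches three months to an outcome whose missingness it reports at months 3, 9 and 15, all of them post-baseline. Both labels cannot describe the same post-baseline variable.

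**The case against.** **The magnitude is built on assumptions.** This is fair. The significance level, number of tests, decision rule and correlations are all supplied here. The 0.5 to 0.85 range comes from correlating log(1 + count) with zero-binge status under assumed negative binomial counts. That is a correlation between outcomes at one visit, not between test statistics from a mixed model and a logistic model. It also depends on how dispersion is defined: 0.52 to 0.84 if it is the size parameter, 0.41 to 0.83 if it is overdispersion. The wider 8% to 14% range does not rest on that step.

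**Section 2.3 already names a primary outcome.** It uses the singular, which a reader might take as a ranking or as a contradiction of Section 1.1. It supports neither. It stands only in the missingness paragraph, may mean one primary among several, and does not say whether the EDE or EDE-Q count is meant.

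**The window is a slip of wording.** Quite possibly: it may be a baseline label carried over. A reader might infer that the window behind the analyses is unknowable or that the wrong one was used. The documents do not support that, because Section 1.2 gives an express definition. What stands is a one-line inconsistency to correct and confirm.

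**Missing data were addressed.** Largely so. Intent-to-treat is defined as all randomized persons, the mixed models use all available data, and the checks in Sections 2.3 and 2.4 are reassuring. What remains is that no analysis is named as lead, and that the all-available-data statement covers continuous outcomes only and so leaves out remission.

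**Conclusion.** The point holds and should be acted on. The primary tier is unranked, with no multiplicity rule, named contrast or lead population. With three primaries tested unadjusted, the chance of a false primary claim is about 8% to 14% instead of 5%, under the assumptions in the working. The binge-window inconsistency is separate and smaller.

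Two stronger readings should be resisted. One could count four to eight measures, three visits and two populations, reach 24 or 48 tests, and quote 71% or more for independent tests. The documents do not say that each such test could carry a primary claim. Visits are also correlated, and the two populations overlap heavily. One could also conclude that every choice was made after the results were known. The text is retrospective and reports missingness results, but it neither shows nor excludes an earlier dated plan that fixed some of these choices.

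**What to change.** 1. **Window.** Reconcile Section 2.3 with Section 1.2 and confirm that the past-month window was used in the post-baseline analyses. Re-run the binge models only if it was not.
2. **Family.** Unless an earlier dated plan sets another, fix three primary outcomes: EDE binge frequency, binge remission and EDE-Q total. Apply Holm at two-sided 0.05 (smallest p-value below 0.0167, next below 0.025, last below 0.05). Label the EDE-Q subscales and EDE-Q binge count supportive.
3. **Contrast.** For each primary, test the treatment difference averaged over months 3, 9 and 15. Do not count baseline as a post-treatment level of time; for the continuous outcomes, for example, enter the baseline value as a covariate. Give visit-specific estimates with confidence intervals as supportive.
4. **Population.** Name intent-to-treat (all randomized) as lead and completers as supportive, and state the population for the logistic remission model.
5. **Provenance.** For each choice separately, cite the dated plan that set it or label it post hoc. Where results are reported, show adjusted beside unadjusted p-values.

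**Cost.** No new data: clarified text, re-tabulated p-values and a disclosure, plus re-fitting wherever the contrast or window used differs from the above. Fewer results can be called primary findings, and choices made now cannot restore prespecified error control.

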### 1.2 Diagnostic and Primary Outcomes: Eating Pathology and Binge Eating

Eating Disorder Examination-Interview 17.0th Edition (EDE)[1] is the structured diagnostic interview that is considered the gold-standard to diagnose, and assess the symptoms of, eating disorders including binge eating and eating disorder pathology. Binge Frequency was defined as the average number of monthly binge episodes for the past three months at baseline, and average number of monthly binge episodes for the past month at post-treatment and follow-up assessments. Binge Remission was defined as zero binge episodes in the previous month.

Eating Disorder Examination-Self-report Questionnaire (EDE-Q)[2] is the self-report version of the more intensive EDE interview. Research has documented that the EDE-Q performs well as a measure of change in treatment trials[3] and has adequate convergence with the interview format[4, 5]. The EDE-Q generates the same frequency data for binge eating in the past 28 days, as well as a total score for overall eating pathology and subscale scores for dietary restraint, weight concern and shape concern, and eating concern.

### 1.3 Secondary Outcomes: Mental Health, Quality of Life and Other Eating Behaviors

The Patient Health Questionnaire-9 (PHQ-9)[6] is a 9-item self-report questionnaire used to assess for the presence and severity of the symptoms of depression. The PHQ-9 has been shown to be a reliable and valid measure of depression severity [7]. The PTSD Checklist (PCL-5)[8] is a 20-item self-report measure assessing the 20 DSM-5 PTSD symptoms. The Weight and Eating Quality of Life (WE-QOL)[9] is an 8-item self-report instrument for measurement of the impact weight and eating has on quality-of-life outcomes [9]. The European Quality of Life (EQ-ED-5L)[10] is a 5-item self-report instrument for measurement of quality of life outcomes that has specifically been used in weight loss trials with Veterans[11]. The Loss of Control Eating Scale (LOCES)[12] is a 7-item scale assessing the sense of loss of control overeating, an important BED characteristic. The LOCES has proven to be valid and is significantly correlated with eating disturbances, general distress, functional impairment, and general self-control [12]. The Night Eating Questionnaire (NEQ)[13] is a 14-item self-report questionnaire used to measure the severity of Night Eating Syndrome. Finally, the Modified Yale Food Addiction Scale 2.0 (mYFAS 2.0)[14] is a 13-item self-administered scale used to assess the features of food addiction. Lower scores reflect better functioning on mental health, WE-QOL, and eating behavior measures; higher scores reflect better functioning on the EQ-ED-5L measure.

### 1.4 Weight Outcomes

Weight Control Strategies Scale (WCSS)[15] is a self-report instrument that assesses the use of specific weight loss behaviors. The measure has been shown to be valid, reliable, and predictive of weight loss [15]. Percent

Weight Loss and 5% Weight Loss. Height at baseline, and weight at every assessment point, were measured with clinic scales for the in-person cohort and at home for the virtual cohort. Veteran MOVE! participant self-report of heights and weights have been shown to be reliable [16]. Percent weight loss was calculated with baseline weight minus the assessment weight and then dividing that number by the baseline weight. This percentage was dichotomized to create a 5% weight loss variable.

### *1.5 Treatment Fidelity*

Treatment Satisfaction for all participants was assessed with an 11-item measure asking patients about their ability to manage aspects of their eating, weight and mental health after treatment, and satisfaction with the treatment, materials, clinician and overall results. Items were rated on a 5-point scale from strongly agree to strongly disagree with higher scores representing greater satisfaction. CBT Treatment Session Attendance for the experimental condition was determined by the number of the nine offered clinician-led CBT treatment sessions attended. CBT Therapist Adherence for the experimental condition was determined by independent assessors who listened to every session of a therapist's first case and then randomly selected audio recordings for 10% of CBT sessions thereafter. Recordings were rated on 13 dichotomized items covering therapeutic alliance, session content (skills), homework and goal setting, and session management. Mean scores resulted in totals ranging from 0 to 1 with higher scores representing greater adherence.

### *1.6 Randomization*

Stratified randomization (clinical BED (n=101) and subclinical BED (n=8)) to the two conditions was performed with a computer-generated sequence.

### *1.7 Treatment Conditions*

#### MOVE! (Treatment-as-Usual)

All participants received VA's Weight Management Program, MOVE!, as administered at their site, without research staff involvement. MOVE! is an evidence-based behavioral weight management program that includes treatment procedures, clinical algorithms, patient and provider information, and instructional materials. The program was widely disseminated and implemented beginning in January 2006 [17]. The 60-minute groups cycle every 16 weeks and are led by trained and monitored MOVE! clinicians who are from the following disciplines: primary care, psychology, nutrition, and physical therapy. Clinicians utilize materials available in hard copy or on-line, and encourage the use of, but do not require or provide, food diaries. Due to the COVID-19 pandemic, MOVE! modalities offered for the present study were expanded to include VA's virtual MOVE! and TeleMOVE! programs. Virtual MOVE! involves synchronous delivery of MOVE! groups via VA Video Connect (i.e., telehealth). TeleMOVE! involves asynchronous delivery of MOVE! content via home-based technology and as needed clinician phone contact. Thus, MOVE! in the present study involved two cohorts: 1) **in-person** MOVE! (n=40), and 2) **virtual** MOVE! or TeleMOVE! (n=69).

#### Brief, Clinician-led Cognitive-Behavioral Therapy for BED

One-half of participants received CBT in addition to MOVE!. The CBT was administered via 9 hourly individual sessions over a three-month treatment period. The treatment was led by a licensed clinical psychologist or social worker following a CBT for BED manual specifically developed for this project. Based upon a manual from previous studies [18, 19], the manual was adapted for the VA healthcare user population using iterative input from VA clinicians experienced with Veteran and eating disorder care, a Veteran Engagement Group paid to provide investigators with feedback about the design of Veteran research, and a Veteran who served as one of the study clinicians for this project. The most notable adaptions included person-first language, Veteran-centered examples, graphical representation of concepts, and writing at the seventh-grade reading level. Four clinicians received training from the Principal Investigator (PI; RM), feedback on videorecording of every session for clinicians' first two cases, feedback and adherence ratings of 10% of sessions thereafter, and weekly supervision from the PI (RM). Participants completed daily records of food intake and binge episodes, and these were reviewed and checked weekly by clinicians. The treatment consisted of three overlapping phases. The first phase involved building a collaborative therapeutic relationship, educating the patient about the diagnosis of BED and maintaining factors of binge eating, and utilizing

behavioral strategies (self-monitoring and goal setting and problem-solving to achieve structured patterning, timing and settings for eating). The second phase integrated cognitive skills such that patients learned to identify and challenge maladaptive thoughts and emotional triggers related to eating/restriction and weight/shape. The final phase focused on the maintenance of change and relapse prevention. Brief clinician-led CBT was conducted in-person before the onset of the COVID-19 pandemic and by phone after.

## 2. Statistical Analysis Plan

Baseline characteristics were compared between the treatment groups using ANOVA and chi-squares as appropriate in order to determine the level of success of the randomization. Distributions of outcomes were examined to determine if assumptions of specific model types were met. Change of model type as well as transformation of the data were considered if model assumptions were not met. Mixed-effects models, a method for statistical modeling that uses both fixed effects and random effects, were used to examine continuous outcomes such as eating pathology binge eating frequency, mental health symptoms, and percent weight loss for completer, as well as intent-to-treat (all randomized persons), analyses. Logistic regression models were used for categorical outcomes such as binge remission and achieving clinically meaningful weight loss (i.e., 5% weight loss or greater). The outcomes were transformed to approach normality as needed and models controlled for treatment, time, gender, age, and baseline BMI.

*2.1 Cohort (in-person vs remote) analyses.* There were 40 (37%) subjects in cohort 1 and 69 (63%) in cohort 2. All the analyses with cohort (categorical variable) added to the models were run and conclusions were substantively the same.

*2.2 Missing Data.* Missing data was minimized by having participants complete with assistance of research assistants. The mixed-effects models addressed missing data for continuous outcomes as the modeling makes use of all available data for each participant, even when there are different numbers of observations. [79]

*2.3 Missingness analyses.* We focused on the missingness of the primary outcome averages binge per month (over past 3 months). Outcome was missing for 11.9% of subjects at month 3, 19.3% at month 9, and 24.8% at month 15. Overall, these 3 timepoints, 35.8% of subjects had incomplete outcome data (missing outcome at any of timepoints). There was no evidence of a difference between groups in missingness at any timepoint or overall (all p-values $\geq$ .10).

*2.4 Variables predictive of missingness.* Those with incomplete outcome data were more likely to be male (p=.05) and younger (p=.01), and have higher baseline BMI (p=0.03), greater highest weight (p=0.01), better weight quality of life at baseline (p=0.03) and lower food addiction at baseline (p=.03). Gender, age, and baseline BMI were already covariates in the models. We repeated the primary analyses to include the other three variables associated with missingness in the models and conclusions stayed the same.

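### The remission model is given as logistic regression with treatment and time but no within-person correlation, analysis set or missing-data rule; pooled literally over three visits, its treatment test is too liberal

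*Combined protocol and SAP*

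**What the plan says.** The combined protocol and SAP defines remission in section 1.2, under the heading for diagnostic and primary outcomes: "Binge Remission was defined as zero binge episodes in the previous month". It can be scored at each of the three post-baseline assessments in 1.1 (months 3, 9 and 15). Section 2.3, however, names binge frequency as the primary outcome. The other binary outcome, 5% weight loss, is exploratory: "Weight outcomes were explored" (1.1).

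Section 2 describes mixed-effects models with fixed and random effects for continuous outcomes, and that same sentence names the analysis sets: "percent weight loss for completer, as well as intent-to-treat (all randomized persons), analyses". The next sentence is all that is specific to binary outcomes: "Logistic regression models were used for categorical outcomes such as binge remission and achieving clinically meaningful weight loss". A covariate statement follows that is not restricted to either outcome type: "models controlled for treatment, time, gender, age, and baseline BMI". It contains no treatment-by-time term.

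On missing data, 2.2 opens with a general remark about preventing it, then gives a method for one outcome type: "The mixed-effects models addressed missing data for continuous outcomes". Section 2.3 reports, for binge frequency: "Outcome was missing for 11.9% of subjects at month 3, 19.3% at month 9, and 24.8% at month 15". It adds that "35.8% of subjects had incomplete outcome data", and that missingness did not differ detectably between arms (all p at least .10). Section 2.4 repeats the primary analyses with three further predictors of missingness and does not say whether the remission model was among them.

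**The concern.** Because time is among the covariates and remission is measured three times, the plain reading is one logistic regression on stacked visits. Visits from the same person are correlated, and treatment varies only between people. A model that treats those visits as independent therefore overstates the information about an average treatment effect. With no treatment-by-time term, that average is the only treatment effect the listed model contains.

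A second matter is separate from the first. The intent-to-treat statement and the missing-data statement are both written for continuous outcomes. The reader cannot tell whether remission was analysed in observed cases, completers or all randomized persons, or how someone with no follow-up interview was counted.

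At stake are the p-value and confidence interval for a clinically prominent binary outcome, and whether the size of the remission difference holds up once dropouts are included.

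**Working it through.** **1. Reproduce the plan's missingness figures.** N = 101 + 8 = 109 (section 1.6).

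| Visit | Missing | Percent | Observed |
|---|---|---|---|
| Month 3 | 13 | 13/109 = 11.9% | 96 |
| Month 9 | 21 | 21/109 = 19.3% | 88 |
| Month 15 | 27 | 27/109 = 24.8% | 82 |
| Any of the three | 39 | 39/109 = 35.8% | 70 complete |

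All four percentages match 2.3. Observed person-visits: 96 + 88 + 82 = 266. These counts are for binge frequency; I take remission to be missing for the same people.

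**2. Pooled fit without clustering: formula.** For a treatment effect averaged over visits, the variance is understated by about DE = 1 + (m − 1)ρ. Here m is the number of visits per person and ρ the within-person correlation of remission, which is assumed. The true two-sided level of a nominal 5% test is 2[1 − Φ(1.96/√DE)].

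With the mean m = 266/109 = 2.44:
- ρ = 0.2: DE = 1.288, level 8.4%
- ρ = 0.3: DE = 1.432, level 10.2%
- ρ = 0.5: DE = 1.720, level 13.5%

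Unequal numbers of visits raise this, because the relevant m is Σm²/Σm. The 70 complete people contribute 70 × 9 = 630 to Σm² and 210 visits. The other 39 share 266 − 210 = 56 visits, which adds between 90 (17 people with two visits, 22 with one) and 112 (28 with two, 11 with none). So m lies between 720/266 = 2.71 and 742/266 = 2.79. The level is then about 9.1-9.3% at ρ = 0.2 and 15.0-15.5% at ρ = 0.5.

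**3. Pooled fit without clustering: simulation.** Each setting had 4,000 null trials with a logit random intercept, missingness correlated across visits and unrelated to outcome, three person-level covariates, and assumed arms of 55 and 54.

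| Assumed remission | ρ | Unclustered, visit-averaged | Cluster-robust |
|---|---|---|---|
| 42-45% | .20 | 9.7% | 6.0% |
| 42-45% | .31 | 11.1% | 5.3% |
| 42-45% | .41 | 15.2% | 5.7% |
| 42-45% | .52 | 16.2% | 5.4% |
| Lower (22-35% range) | .19 | 8.4% | 5.2% |
| Lower (22-35% range) | .39 | 13.8% | 5.2% |
| Lower (22-35% range) | .50 | 15.3% | 5.8% |

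Monte Carlo error is about 0.3-0.6 points. When treatment-by-visit is added and a single visit is tested, the same unclustered fit stays at 4.0-6.0%. The inflation therefore belongs to the visit-averaged effect only.

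**4. Dropouts at month 15: illustration.** Assume remission of about 50% v 25% among those observed, arms of 55 (CBT) and 54 (MOVE!), and missing counted as not remitted. Tests are uncorrected chi-square.

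| Missing, CBT v MOVE! | Observed cases | Over all randomized |
|---|---|---|
| 13 v 14 | 21/42 v 10/40: 25.0 points, p=.020 | 21/55 v 10/54: 19.7 points, p=.023 |
| 14 v 13 | 20/41 v 10/41: 24.4 points, p=.022 | 20/55 v 10/54: 17.8 points, p=.037 |
| 17 v 10 | 19/38 v 11/44: 25.0 points, p=.019 | 19/55 v 11/54: 14.2 points, p=.098 |
| 10 v 17 | 22/45 v 9/37: 24.6 points, p=.022 | 22/55 v 9/54: 23.3 points, p=.007 |

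The last two rows are the most uneven splits that still give p at least .10 for a difference in missingness (p=.134 and .108). In the 14 v 13 row, half of 41 is 20.5 and was rounded down; rounding up gives 21/55 v 10/54, p=.023.

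**The case against.** The strongest reply is that the text is terse and not wrong. Listing time may be shorthand for a mixed logistic model or a GEE, and the document excludes neither. The error inflation also needs two things together: an unclustered pooled fit and a test of one averaged effect. Separate fits by visit, or visit-specific contrasts, escape it. This stands, and it makes the 8-16% conditional. It does not remove the point, because the model as listed has no interaction term and no clustering, and the random effects are expressly placed with the continuous outcomes.

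A second reply is that other sections cover the binary models. Section 2.1 reruns all the analyses with cohort added, which must include them, and 2.4 may include remission. Both add covariates. Neither supplies a correlation structure, an analysis set or a rule for missing remission.

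A third reply is that observed-case logistic regression is valid if missingness depends only on arm and modelled covariates, and gender, age and baseline BMI were in the models. That is right. A reader might infer that dropout biased the remission result or that its significance hinges on how dropouts are counted. The documents support neither. In the illustration, significance survives near-even dropout and is lost only at a split that 2.3 permits but does not indicate. Other assumed rates do not make the case stronger. For 45% v 25% at the 17 v 10 split, p moves from .060 to .208, so it was not significant before any dropout was counted.

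**Conclusion.** The point holds in a conditional form. As written, the remission analysis is a logistic regression on repeated visits with no allowance for within-person correlation. If that model was fitted and its single treatment effect tested, type I error is roughly 8-16% at correlations of about 0.2-0.5, against about 5-6% with cluster-robust standard errors. The rates, correlations and arm sizes are all assumed.

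Separately, no stated analysis gives the remission result over all 109 randomized persons, although up to 27 are missing at one visit. With 50% v 25% observed and missing counted as not remitted, the month-15 difference falls from about 25 to about 18-20 points at near-even dropout (p about .02-.04). This is sensitivity, not demonstrated bias.

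It would go too far to infer that the reported remission finding is a false positive, since the document does not show which model was run. Nor should this be called a flaw in the analysis of the primary outcome without qualification: remission sits under the primary-outcomes heading, but 2.3 gives that role to binge frequency. For 5% weight loss the model point applies to an exploratory outcome only. Overall this is an inexpensive improvement, held with medium confidence.

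**What to change.** - **Model.** Analyse remission, and 5% weight loss as exploratory, with a logistic GEE with robust standard errors or a logistic mixed model over all available visits. Include treatment, visit, treatment-by-visit and the existing covariates.
- **Contrast and analysis set.** State whether the test is at one named visit or averaged over visits, and which participants it includes.
- **Sensitivity analysis.** Add an analysis of remission over all 109 randomized persons by multiple imputation within arm, using the predictors of missingness in 2.4. Counting missing as not remitted is an optional stress test and is deliberately not neutral.
- **Section 2.4.** Include the remission model in the repeat analysis, or say that it was included.

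The cost is SAP wording and a modest amount of extra analysis in standard software, with no new data. If visits had been pooled without clustering, the interval for the averaged effect becomes wider. In the simulation at 42-45% remission, empirical SD over model standard error was .305/.257 = 1.19 at correlation .20 and .361/.257 = 1.40 at .52, so about 19% to 40% wider. If a clustered model was already used, the model description needs only a wording change, and the all-randomized analysis is the substantive addition.
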